Pediatric Inpatient Firearms Study

Principal Investigator: [name]
Co-Investigators: [name]
[name]
[name]
[name]
[name]
[name], MS4
[name], MS4

BACKGROUND

The United States (US) is the only developed country in which firearm violence is a major cause of death. Of all firearm deaths in high-income countries, 80% occur in the US.¹ Gun violence remains a top killer of young people in the U.S. In the year 2014, 2,549 young people (ages 0-19 years) were killed with a firearm in the US, most of whom were 15-19 years.² Firearm injuries and deaths can be categorized as homicides, suicides, unintentional shootings, legal intervention (police involvement), or undetermined. Unintentional shootings comprise 4% of all pediatric firearm deaths and often involve young children. Homicide and suicide, which comprise 94% of pediatric gun death, overwhelmingly affect teens.³ Urban teen males suffer from high rates of gun homicide, while rural teen males die from gun suicide.⁴

In addition to the pediatric mortality associated with firearm violence, firearm injuries leading to hospitalization and other morbidities are a substantial public health issue that is less well-studied. In 2009, there were over 7300 hospitalizations of children and adolescents due to firearm injuries in the US, with nearly 3 children per day under the age of 15 being hospitalized for firearm related injuries.⁵

The American Academy of Pediatrics recommends a firearm-free household as the safest environment for children and teens. For families that own guns, safe storage with gun and ammunition kept locked in separate compartments protects young people from unintentional or intentional violence.³ Studies of safe storage counseling have yielded mixed results. These interventions tend to focus on gun-owners, with counseling specifically on safe storage of firearms. There is a dearth of randomized-controlled trials on this subject.⁶

Everytown for Gun Safety is a group that was founded in the wake of the massacre at Sandy Hook Elementary School in order to work for safer gun laws and promote safe storage of firearms. They have created a non-political, non-legislative gun safety campaign called “Be SMART” to promote the principles of safe firearm practices in the home.⁷ The campaign focuses on the responsibility of the adult to practice firearm safety, rather than asking children to behave responsibly around

firearms since this has been proven to be an ineffective strategy.⁸ It also provides counseling for non-firearm-owning families, as it recommends asking about unsecured firearms prior to playdates. Thus, it can serve as a simple, universal counseling tool for parents who are gun-owning and non-gun-owning. It has not been formally evaluated as an educational tool.

Children's hospitals may be a good place to counsel on firearm safety. Large children's hospitals draw patients from surrounding areas that may include rural, suburban, and urban areas. A hospital-based intervention would allow outreach to children of all ages. The "free time" patients spend in the hospital, while either recovering or waiting for procedures or results, may make patients amenable to receiving such counseling. The inpatient setting has been successfully utilized to provide educational interventions to parents of hospitalized children on other topics, best studied in the area of smoking cessation.⁹⁻¹² Walley et al. utilized the "Smoking and Kids Don't Mix" video for parents/caregivers of hospitalized children, demonstrating successful reported behavior changes in parents/caregivers to reduce second- and third-hand smoke.¹² To our knowledge no other study has utilized the inpatient setting to address issues related to firearm safety counseling and education.

The primary aim of the study is to determine whether the Be SMART campaign delivered to parents in a hospital setting leads to an improvement in knowledge, attitudes, and practices about firearm safety. The secondary aim is to determine whether the intervention is more effective when delivered with physician face-to-face counseling in addition to with video and written materials, or with standardized video and written materials alone.

Study Aims:

- 1) To measure whether parents' knowledge, attitudes, and practices change after a brief educational intervention on gun safety
- 2) To measure the knowledge, attitudes, and practices of parents in a tertiary care children's hospital regarding firearm safety practices
- 3) To compare the efficacy of two methods of delivery of counseling: a video alone versus a video plus a physician-delivered intervention
- 4) To measure whether these changes in practices are sustained one month after the intervention

METHODS

Study Design: This is a randomized controlled 3-arm pre-/post-intervention study to investigate the effect of an educational intervention using a Be SMART video and written material on parental/legal guardian knowledge, attitudes and practices regarding firearm safety. An additional element of the study design includes a randomized controlled trial to investigate any additional effect of a pediatrician-delivered educational intervention on parental/legal guardian knowledge, attitudes

and practices regarding firearm safety. Given that tobacco smoke exposure interventions have been previously studied in hospitalized children, we will use a video and written materials on tobacco smoke exposure education as our control group.¹² We will use survey techniques to determine baseline and post-intervention knowledge, attitudes and practices regarding firearm safety in parents/legal guardians of hospitalized children <20 years old.

Study population: Parents/legal guardians of children <20 years old hospitalized at CHAM.

Inclusion criteria: All parents/legal guardians of children <20 years old hospitalized at CHAM who reside with the child.

Exclusion criteria: Previously enrolled in the study, parent/legal guardian preferred language other than English or Spanish, hospitalized in the Pediatric Intensive Care Unit/critically ill child, or parent/legal guardian acutely distressed.

Study procedure: Daily, residents on the primary medical team will ask the parents/legal guardians of new patients or parents/legal guardians not previously enrolled in the study if they would allow research personnel to speak with them about the study. If the parent/guardian allows, study personnel will then attempt to approach all parents/legal guardians of children <20 years old using the attached "Research Personnel Script" and the "Eligibility Form" to assess eligibility. If eligible for the study, the participant will then be approached for informed consent. If they consent, study personnel will conduct a standardized verbally-administered "Initial Parent/Guardian Survey". Once the survey is complete, the participant will be randomized to one of 3 study groups: 1. Be SMART alone group: To view the Be SMART video and to receive Be SMART written material alone, 2. Be SMART + MD group: To view the Be SMART video and to receive Be SMART written material and subsequent standardized reinforcement/review with a pediatrician using the "MD Checklist for Intervention Review" or 3. Control Group: To view the "Kids and Smoke Don't Mix"¹² and to receive written materials from the New York State Smokers Quitline. Study participants will be randomized in blocks of 15 by www.randomization.com. For patients in the "Be SMART+MD" group, each physician will verbally review all 5 elements of Be SMART in person with the participants, as denoted in the attached checklist.

Following the intervention, study personnel will conduct a brief verbally administered "Post-intervention Parent/Guardian Survey". One month later, study personnel will conduct the "One Month Follow-up Parent/Guardian Survey" verbally administered via telephone.

Survey Instruments: See attached surveys:

1. Inpatient Firearms Study—Eligibility Form
2. Inpatient Firearms Study—Initial Parent/Guardian Survey
3. Inpatient Firearms Study—Post-intervention Parent/Guardian Survey

4. Inpatient Firearms Study—One Month Follow-up Parent/Guardian Survey
5. Inpatient Firearms Study—Research Personnel Script

The questions in all of the Parent/Guardian surveys (Initial, Post-intervention and One Month Follow-up) were all adapted from prior published studies which used surveys addressing the topic of youth firearm exposure and safety,¹³⁻¹⁷ and the control tobacco exposure questions adapted from other published studies on tobacco smoke exposure in children.¹²

Intervention Checklist: See attached—Inpatient Firearms Study—MD Checklist for Intervention Review.

Outcomes:

The primary outcome is the change in parent/legal guardian's behavior over the past 30 days with respect to how often they asked whether or not there are guns in the home when their child/children goes to play in another's person's home, as indicated by a Likert scale assignment of an ordinal value (1-5, 1= never, 2=rarely, 3=sometimes, 4=most of the time, 5=always).

Secondary outcomes will include:

- Change in the primary outcome (intention to ask noted above) between the intervention groups (Be SMARTalone vs. Be SMART + MD)
- Demographic factors associated with primary outcome
- Description of general knowledge on firearm safety of parents/legal guardians of patients in our community
- Description of attitudes about firearm safety of parents/legal guardians of patients in our community
- Description of general practices regarding firearm safety of parents/legal guardians of patients in our community
- Description of parents attitudes regarding physicians discussing firearm safety with them

Data Analysis:

The main objective of the data analysis is to assess within each intervention group whether the general parental practice of asking about firearms in the homes of others when their children go to play is increased after the intervention. A secondary objective is to perform a head-to-head comparison of the magnitude of the intervention effects between the groups. Our pilot data revealed the proportion of the population who either "always" or "most of the time" ask about firearms in the homes of others when their children went to play was 50%. With a sample size of 60 subjects in the Be SMART alone group, the study will have 80% power using the McNemar's test with a two-sided alpha=0.05 level to detect an absolute increase of 20% between the pre-intervention and post-intervention responses (i.e. raising the proportion of those who either "most of the time" or "always" ask about firearms in the homes of others when their children went to play from 50% to 70%). For the

Be SMART + MD group, we expect the pre- post intervention effect to be larger, i.e., increase from 50% before the intervention to 80% after the intervention in the proportion of the population who either “most of the time” or “always” asked about firearms. With a sample size of 60 subjects in the Be SMART + MD group , the study will have greater than 95% power to detect this difference using the McNemar’s test with a two-sided alpha=0.05 level. We expect minimal change in the pre- and post-survey responses in the control group. For the comparisons between treatment arms, we will focus on the subset of parents who initially responded that they were not likely to ask about firearms before the intervention (expected to be ~ 50% of parents) and assess whether the proportion who changed their response to “most of the time” or “always” after the intervention is greater in those who were in either of the Be SMART groups compared to the control group. With 60 subjects in each of the 3 study groups, the study will have 80% power to detect an increase in this proportion from 10% in the control group (which is a conservative assumption) to 40% in either the Be SMART alone or Be SMART + MD group using a two-sample test of proportions and a two-sided alpha=0.05 level.

We anticipate the majority of the subjects enrolled will complete the inpatient portion of the study, however, we estimate up to 20% will not be able to be reached by phone for the 30 day follow up call. Therefore given that our primary outcome is based on behavior assessed at the 30 day follow up phone call, we will add to each study group 15 patients to give each study group at total of 75 patients, and the overall study population will be 225 patients.

For within-group data analysis, we will use standard descriptive statistics to summarize the data and McNemar’s test or the paired T- test to assess the significance of pre-post intervention differences in binary and continuous outcomes, respectively. In secondary analysis, we will analyze the parents who responded before the intervention: “rarely”, “never”, or “sometimes” to ask about firearms in the homes of others when their children went to play groups and compare across interventions the proportion who changed their response to “most of the time” or “always” after the intervention using the chi-square or Fisher’s exact test. We will also use logistic regression models to analyze factors associated with the likelihood to ask about firearms in the homes of others when children go to play.

Informed Consent:

Parents of hospitalized children will be approached for written informed consent on the inpatient service by trained research personnel. Our form asks for consent to participate in the pre-intervention and post-intervention surveys, and to participate in the educational intervention, including randomization to one of the three study groups (Be SMART alone, Be SMART+ MD discussion, or the control group). Additionally the consent asks for permission to collect phone numbers in order to contact the parent/legal guardian one month later for a follow up survey. If consent is granted, a brief questionnaire will be administered followed by the intervention and very brief follow up survey.

Risks:

We do not anticipate any risks to the participants. Any information obtained that would permit identification of a participant, it will be held strictly confidential, will be used only for the purpose of this study, and will not be disclosed or released to others.

Benefits:

This study will examine knowledge, attitudes, and practices of parents/legal guardians regarding firearm safety and tobacco smoke exposure. While there may be no direct benefits to the participants themselves, through the educational intervention, they may increase their knowledge regarding gun safety and tobacco smoke exposure, particularly related to children, and may decide to change some of their own practices related to either or both firearm safety issues and tobacco smoke exposure and their children.

Privacy:

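### As written, the eligibility and procedure text lets two parents of one child be randomised to different arms, which could slightly dilute the secondary between-arm comparisons

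*Combined protocol and SAP*

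**What the plan says.** Under Inclusion criteria the plan admits "All parents/legal guardians of children <20 years old hospitalized at CHAM who reside with the child". The Exclusion criteria begin "Previously enrolled in the study, parent/legal guardian preferred language other than English or Spanish". The first item does not say whether the parent, the child or the family must not have been enrolled before.

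Study procedure supplies a subject: residents ask permission from parents of new patients or from "parents/legal guardians not previously enrolled in the study". It continues: "study personnel will then attempt to approach all parents/legal guardians of children <20 years old". After the initial survey "the participant will be randomized to one of 3 study groups", and "Study participants will be randomized in blocks of 15". No family or household stratum is mentioned, and no rule places co-parents in the same arm.

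The primary outcome under Outcomes is the change in each parent's own "behavior over the past 30 days with respect to how often they asked" about guns in other homes. The main analysis is pre-post within each group. Comparisons between arms are secondary, and Data Analysis plans them with a chi-square or Fisher's exact test. The Privacy section says that subject numbers are not linked to the hospitalised child.

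**The concern.** Two parents who live with the same child can each be approached, consent and be randomised. If one is assigned a Be SMART arm and the other the tobacco control, they go home to the same household with a short, easily repeated message and written material. They then have about a month before the follow-up call. A control parent who picks up the message looks more like a Be SMART parent, and the difference between the arms shrinks. The same can happen between Be SMART alone and Be SMART + MD.

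The comparisons exposed are those that use the randomisation. The Be SMART versus control comparison is planned at 80% power in roughly half of each arm, so it has little reserve.

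A second, smaller issue is that two parents of one child may answer alike, while the chi-square, Fisher, logistic and McNemar analyses all treat participants as independent. Without a link to the child, pairs could not readily be identified later.

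**Working it through.** **Inputs from the plan (Study procedure and Data Analysis).** Blocks of 15; three groups of 75, taken as equal allocation, so 5/5/5 in each block; 60 per group after 20% loss (60/0.80 = 75); about 50% of parents in the between-arm subset; change rates of 10% (control) and 40% (Be SMART); two-sided alpha 0.05; stated power 80%.

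**Assumptions, not in the plan.** *f* is the share of participants who have an enrolled co-parent. *c* is the share of the 30-point effect passed on to a control co-parent.

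**1. The plan's own figure.** The subset is 60 × 0.50 = 30 per arm. Power for 10% versus 40% at 30 per arm is 78.0% by the pooled normal formula, 81.6% by the unpooled formula, and 79.6% by exact enumeration of the chi-square test. The stated 80% is reproduced. The 79.6% figure is the baseline below.

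**2. Chance that co-parents are split.** In the same block, once the first parent is placed, 10 of the remaining 14 slots belong to other arms: 10/14 = 71%. In separate blocks it is 2/3 = 67%. If the first parent is a control, any split puts the other parent in a Be SMART arm.

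**3. Diluted control rate.** Control rate = 0.10 + *f* × (10/14) × *c* × 0.30. With *c* = 0.5:
- *f* = 2%: 0.10 + 0.02 × 0.714 × 0.5 × 0.30 = 10.2%
- *f* = 5%: 10.5%
- *f* = 10%: 11.1%

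**4. Power against 40%, 30 per arm, exact enumeration.**

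| Share in pairs | Same block | Separate blocks |
|---|---|---|
| 0% | 79.6% | 79.6% |
| 2% | 78.8% | 78.9% |
| 5% | 77.6% | 77.8% |
| 10% | 75.6% | 75.9% |

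**5. In people.** Exposed controls among the 30 analysed = 30 × *f* × (10/14): about 1.1 at 5% and 2.1 at 10%.

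**6. What a larger loss would take.** At half transfer, a loss of 5 power points needs about 12% of participants to be in pairs.

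The plan states no power for Be SMART alone versus Be SMART + MD, so dilution of that comparison is not quantified. Nor is the effect of correlated answers, since the documents give no correlation.

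**The case against.** **The rule may already exist.** The exclusion list mixes parent-level items with a child-level one (intensive care or critical illness), so prior enrolment could be meant at child level. The sample size is counted in patients, which fits one enrolment per child. The reference to all parents may describe the eligible population and not instruct staff to enrol both members of a couple. The Eligibility Form is listed as attached but was not supplied. A reader might infer that the trial has no such rule, or that couples were in fact enrolled; the documents support neither. What stands is that the one place giving prior enrolment a subject, Study procedure, names the parent or guardian, and that the word patients is also used there for participants, who are parents.

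**The loss is small.** At 2% to 5% in pairs with half transfer, it is 0.8 to 2.0 points, less than the 3.6-point spread between the pooled and unpooled formulas (78.0% and 81.6%). This stands, and it keeps the severity low. One can obtain power near 63% by assuming 20% in pairs and full transfer, but nothing in the documents supports those values.

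**The timing is not certain.** The secondary outcome reads "Change in the primary outcome (intention to ask noted above) between the intervention groups", and the between-arm test refers only to responses after the intervention. If the immediate inpatient survey were used, there would be far less time to share. Data Analysis does tie the primary outcome to the 30-day call and sizes each group for loss at that call, so the 30-day reading is the more natural one. The dilution argument depends mainly on it.

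**The main objective is untouched.** A reader might infer that the primary result is compromised. It is not directly biased by sharing between arms: the Be SMART tests compare each parent's answers with that parent's own earlier answers.

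**Conclusion.** The concern holds in limited form, as a point to consider. The supplied text, followed literally, allows co-parents of one child to be placed in different arms, with probability 71% or 67% once both enrol. The likely consequence is a slight dilution of the secondary between-arm comparisons. That direction is plausible but not certain, because the outcome is each parent's own asking.

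The illustrated loss is 2.0 power points at 5% in pairs (79.6% to 77.6%) and 4.0 at 10% (to 75.6%). Both rest on an assumed pair share, an assumed half transfer and use of the 30-day responses. The true size cannot be derived from the documents. Correlated answers are a further reason not to enrol pairs, of unknown size. The point is worth raising because prevention costs almost nothing.

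**What to change.** - Amend the Inclusion criteria to enrol one parent or guardian per hospitalised child or household.
- Give the first exclusion a subject, for example: this parent, or another parent or guardian of this child or household, previously enrolled.
- Align the wording in Study procedure with it.
- Confirm that the Eligibility Form asks this before consent, or add the question.

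**Cost:** one line in the criteria and at most one screening question. The sample size stays at 75 per group and 225 overall, and no child identifier has to be stored. Some willing second parents would not be enrolled, so accrual may be slightly slower.

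A later analysis that removes split pairs is not requested. It would recover almost no power, and finding the pairs would mean using the name and phone record for something other than the follow-up call stated under Privacy.

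### Does the label intention to ask, with no survey named, leave the between-arm comparison undefined?

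*Combined protocol and SAP*

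**What the plan says.** In Outcomes, the primary outcome is the change in "behavior over the past 30 days with respect to how often they asked" about guns where the child goes to play, scored 1 to 5 from never to always. The first secondary outcome, which contrasts the two Be SMART arms, is "Change in the primary outcome (intention to ask noted above) between the intervention groups". The second is "Demographic factors associated with primary outcome".

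Study procedure schedules two surveys after the intervention: a brief inpatient one and a telephone one a month later.

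Data Analysis states the between-arm aim: "A secondary objective is to perform a head-to-head comparison of the magnitude of the intervention effects between the groups". The within-arm power text speaks of "an absolute increase of 20% between the pre-intervention and post-intervention responses" for the video arm, and of an "increase from 50% before the intervention to 80% after the intervention" for the video-plus-physician arm. For each Be SMART arm against control it says: "With 60 subjects in each of the 3 study groups, the study will have 80% power to detect an increase in this proportion", from 10% to 40%, among parents not asking at baseline.

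On attrition it says "we estimate up to 20% will not be able to be reached by phone for the 30 day follow up call". It gives as the reason for the extra enrolment that the primary outcome is behaviour assessed at that call. The paragraph on methods then describes the between-arm test and the logistic regression without naming a survey for either.

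**The concern.** Intention and past behaviour are different constructs. An intention can be recorded at the bedside straight after a video. A change in 30-day behaviour cannot, because the recall period would lie almost wholly before the intervention.

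The bullet with the wrong label defines a randomized contrast that the Background names as the trial's secondary aim. The loose wording recurs: the power text describes the comparison subset as parents not likely to ask, and the regression models a likelihood of asking. The inpatient form is itself titled Post-intervention, and the consent section lists post-intervention surveys apart from the one-month follow-up.

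If the inpatient response supplied the after value, the randomized comparison would no longer measure the outcome it is built on. With two candidate surveys and neither named, the choice could also be made after the data were seen.

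**Working it through.** **Which construct?** The bullet points back to something noted above it, and the only item above it is the past-30-day frequency question. No intention outcome or intention scale is defined anywhere in the text. The between-arm test takes parents who answered never, rarely or sometimes and counts those who move to the top two categories, so it is scored on the behaviour item's own five-point scale. The subset share agrees: the pilot figure for the top two categories is 50%, and 100% − 50% = 50% is the share the power text assigns to the subset.

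**Which time point?** The attrition paragraph of Data Analysis fixes the primary outcome at the 30-day call. The first two secondary outcomes are defined as features of that outcome and so carry its time point.

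**Does the sizing agree?** The inputs, all from Data Analysis, are 75 enrolled per arm, up to 20% lost at the call, a subset of about 50%, conversion of 10% against 40%, and two-sided alpha 0.05.

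- Reached at the call: 75 × (1 − 0.20) = 60 per arm. Conversely 60 / 0.80 = 75, and 3 × 75 = 225, the plan's total.
- Subset at the call: 60 × 0.50 = 30 per arm.
- Subset if all 75 answered in hospital (an assumption): 75 × 0.50 = 37.5, so 37 or 38 per arm.

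Pooled normal approximation with n = 30 and mean proportion (0.10 + 0.40)/2 = 0.25:

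z = [0.30 × √30 − 1.96 × √(2 × 0.25 × 0.75)] / √(0.10 × 0.90 + 0.40 × 0.60) = (1.643 − 1.200) / 0.574 = 0.77, so power is 0.780.

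Unpooled:

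z = 0.30 / √(0.33/30) − 1.96 = 2.860 − 1.960 = 0.90, so power is 0.816.

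| Subset per arm | Pooled | Unpooled | Exact, uncorrected chi-square | Exact, Fisher |
|---|---|---|---|---|
| 30 (call) | 0.780 | 0.816 | 0.796 | 0.705 |
| 37 (inpatient) | 0.862 | 0.888 | 0.875 | 0.815 |
| 38 (inpatient) | 0.871 | 0.896 | 0.885 | 0.830 |

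The plan's 80%, stated for a two-sample test of proportions with 60 per arm, is reproduced at 30 per arm. The inpatient count would give 0.86 to 0.90 by the same methods. Fisher's test at 37 per arm also falls near 80%, but that needs 75 per arm and a different test, and the power sentence specifies neither.

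**The control arm.** The plan expects little change within this arm, so its 60 parents enter a power statement only through the between-arm comparison. Yet it too is raised to 75 because of loss at the call. That is natural if the comparison is made at the call, although a wish for equal arms could also explain it.

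**The case for a change.** The strongest case for a change is that the time point must be inferred. It appears only where the plan justifies extra enrolment, not in the outcome definition or the methods paragraph. The bullet that refers back to the primary outcome also mislabels it, and Study Aims lists persistence at one month as a separate aim, which suggests that some earlier measurement also counts. Naming the call would cost one sentence.

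Part of this stands: the label is wrong, and the methods paragraph does omit the survey. What does not stand is that the omission leaves two equally good readings. The inpatient reading needs an item on that form able to supply the after value. The survey forms are attachments outside the text reviewed, so this can be neither shown nor held against the plan. It would also set aside the plan's explicit statement about the call.

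The regression is less certain. Its link to the second secondary outcome points to the call, but the text would also allow a baseline analysis serving the descriptive aim. Either is a reasonable supporting analysis, and neither alters the primary result.

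The power of the contrast between the two Be SMART arms is a separate question. Neither the label nor the unnamed survey causes it.

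**Conclusion.** No change follows. The label is a clerical slip, and the missing survey name is a gap that the plan's other statements fill. An analyst who follows the outcome definition, the response categories and the sample-size text will compare the initial survey with the one-month call on the past-30-day item, which is the analysis the concern asks for. New wording would leave 75 per arm, 225 in total and the stated 80% power as they are (0.78 to 0.82 at 30 per arm by chi-square calculations, 0.705 if Fisher's test is used).

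This rests on the plan's own assumptions of 20% loss and a 50% subset, and on taking the call as the time point for every outcome defined from the primary one. Confidence is high for the between-arm test and lower for the regression, where the text does not exclude a baseline analysis.

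### The main analysis is a before-after test inside each Be SMART arm, and the randomised comparison with control ranks only as secondary

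*Combined protocol and SAP*

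**What the plan says.** The Study Design paragraph says "This is a randomized controlled 3-arm pre-/post-intervention study", and for the comparator "we will use a video and written materials on tobacco smoke exposure education as our control group". The Background gives the primary aim as "to determine whether the Be SMART campaign delivered to parents in a hospital setting leads to an improvement" in knowledge, attitudes and practices. Under Study procedure every parent is surveyed first: "Once the survey is complete, the participant will be randomized to one of 3 study groups". A second survey follows the intervention, and a third is done by telephone at one month.

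The primary outcome is a change in how often the parent asks about guns, with no comparator named. Data Analysis then opens: "The main objective of the data analysis is to assess within each intervention group whether the general parental practice of asking about firearms" in other homes increases. The first two power statements are McNemar tests within one arm of 60: 80% power for 50% to 70% in Be SMART alone, and more than 95% for 50% to 80% in Be SMART + MD.

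Between-arm work comes next: "A secondary objective is to perform a head-to-head comparison of the magnitude of the intervention effects between the groups". For parents who were not asking at baseline, each Be SMART arm is compared with control, with 80% power "to detect an increase in this proportion from 10% in the control group (which is a conservative assumption) to 40" per cent. The analysis paragraph ranks this comparison: "In secondary analysis, we will analyze the parents who responded before the intervention" never, rarely or sometimes. The list of secondary outcomes names only Be SMART alone against Be SMART + MD. The plan expects little change in the control arm but attaches no test or decision rule to that expectation.

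**The concern.** Whether Be SMART leads to an improvement is a causal question, and the control arm is there to answer it. A pre/post test within one arm estimates the Be SMART effect plus everything else that moves answers between the bedside survey and the telephone call. Parents in all three arms answer firearm questions before randomisation and again afterwards, so repeat questioning or a wish to give the approved answer could raise reported asking in every arm. A McNemar test within an arm cannot separate such a shift from an effect of the video or the physician. The randomised comparison can.

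If all arms rise together, the main analysis can be positive while the comparison with control is not. The documents do not say which result then decides whether Be SMART works.

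**Working it through.** **Inputs from Data Analysis.** 60 evaluable parents per arm; baseline asking 50%; targets 70% (alone) and 80% (+ MD); two-sided alpha 0.05; about half of each arm not asking at baseline, so 30; conversion among them 10% in control and 40% in a Be SMART arm; 20% loss by day 30.

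**The plan's own figures.**
- Sample size: 60/0.80 = 75 per arm, 3 × 75 = 225. Reproduced.
- McNemar power is Φ[(δ√n − 1.96√ψ)/√(ψ − δ²)], where δ is the net change and ψ the share of parents who change category. The plan gives no ψ. With δ = 0.20, n = 60 and ψ = 0.32: (1.549 − 1.109)/0.529 = 0.83, power 79.7%. So the stated 80% needs ψ of about 0.32. With independent answers (ψ = 0.50) it is 59.5%. For δ = 0.30 and ψ = 0.40, power is 97.4%.
- Control comparison, 10% against 40%, 30 per arm: 79.6% for the uncorrected chi-square test by exact enumeration (78.0% pooled formula, 80.3% arcsine, 81.6% unpooled). The stated 80% is reproduced. Fisher's exact test gives 70.5%.

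**A shift common to all arms, no Be SMART effect.** Take ψ = 0.32 (assumption) and a net shift s. Upward switching is (0.32 + s)/2 and backward switching (0.32 − s)/2. Conversion among non-askers is the upward share divided by 0.5. The chance of a significant increase is by exact enumeration of the uncorrected McNemar test, n = 60. For at least one of the two Be SMART arms it is 1 − (1 − p)².

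| Common shift | Up / back | Conversion of non-askers | One arm | At least one Be SMART arm |
|---|---|---|---|---|
| 0 | 16% / 16% | 32% | 2.6% | 5.1% |
| +5 points | 18.5% / 13.5% | 37% | 10% | 19% |
| +10 points | 21% / 11% | 42% | 28% | 49% |
| +20 points | 26% / 6% | 52% | 83% | 97% |

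**How often the two analyses disagree.** Simulation of 400,000 trials with the same switching in all three arms: at least one Be SMART arm is significant by McNemar, while neither is significantly better than control by chi-square, in 18%, 45% and 92% of trials for +5, +10 and +20 points. If a difference from control in either direction counts, the figures are 17%, 44% and 88%. The control comparison falsely favours a given Be SMART arm in about 2.6% of trials, whatever the shift.

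**The plan's own control assumption in every arm.** 10% of 50% non-askers is 5 points upward. Backward switching is not stated, so it is varied:

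| Points switching back | Uncorrected McNemar, per arm | Exact McNemar, per arm |
|---|---|---|
| 0 | 35% | 8% |
| 1 | 21% | 5% |
| 2 | 12% | 3% |
| 5 (no net shift) | 2% | 1% |

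The nominal rate in the favourable direction is 2.5%.

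**The case against.** The strongest reply is that the plan already holds the remedy. The trial is randomised, and the comparison with control has a stated subset, endpoint, test and power. It will be reported whatever its label, and nowhere do the documents say that a McNemar result alone establishes efficacy. All of that is true. It leaves the ranking where it is: the main analysis ignores the control arm, and nothing settles a disagreement between the two analyses. Reading the phrase about each intervention group to include control does not help, because separate tests in three arms are not a comparison between them.

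The second reply concerns size. The +5, +10 and +20 cases imply that 37%, 42% and 52% of control non-askers convert, against the 10% that the plan assumes and calls conservative, and no document supports a 20-point control shift. This stands: those rows show how the test behaves and do not forecast this trial. The figures built on the plan's own assumption depend heavily on the test variant, which the plan does not name. The 35% needs the uncorrected test, no back-switching and only about 3 changed answers in 60 (0.05 × 60). With exact McNemar the range is 1% to 8%.

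Third, the responder comparison uses about half of the randomised parents and ignores askers who stop. That is a real limit, and it calls for a supportive analysis in all parents. It does not break the randomisation, because the subset is fixed by the survey taken before allocation.

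**Conclusion.** The concern holds. The main analysis of a randomised controlled trial does not use its control arm, and no rule makes the conclusion depend on that arm. This rests on the text alone.

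The numerical size rests on assumptions: 60 evaluable parents per arm, no Be SMART effect, a discordance of 0.32 inferred from the power claim, and hypothetical common shifts. Under the plan's own control assumption the inflation runs from none to substantial, depending on back-switching and the form of McNemar's test. If upward and backward switching balance, there is none. The change has to be made before outcome data are seen, because choosing the deciding analysis afterwards would not be credible.

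**What to change.** Make the plan's own responder comparison primary:

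- **Primary.** Among parents answering never, rarely or sometimes at baseline, compare the proportion answering most of the time or always at the 30-day call, each Be SMART arm against control, Holm-adjusted at two-sided 0.05. Name the test in advance. The uncorrected chi-square test is the one that matches the stated 80%. A fixed order, with or without a pooled first step, is an acceptable alternative to Holm.
- **Secondary.** Be SMART alone against Be SMART + MD.
- **Descriptive.** The within-arm McNemar tests, in all three arms.
- **Supportive.** The 30-day proportion asking in all randomised parents reached, each Be SMART arm against control, so that askers who stop are counted.

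**Cost.** No new data and no more parents, but lower stated power. With 30 non-askers per arm and 10% against 40% in both Be SMART arms:

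| Rule | Power |
|---|---|
| Chi-square, each comparison alone | 80% |
| Chi-square with Holm | 76% per arm, 86% for at least one |
| Chi-square, + MD then alone | 80%, 68% |
| Chi-square, pooled then + MD then alone | 89%, 78%, 68% |
| Fisher, each comparison alone | 71% |
| Fisher with Holm | 65% per arm |

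Holm with chi-square gives 71% if only one arm works, and 69% per arm with 25 non-askers per arm and both working. The cost is smaller on the plan's larger + MD target: 50% to 80% implies at least 0.30/0.50 = 60% conversion, and Holm then gives 99% for + MD and 79% for Be SMART alone.

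The supportive comparison of 60 against 60 has 62% power for 70% against 50% and 94% for 80% against 50%. If control rises to 55% (10% of non-askers converting, none switching back), these fall to 40% and 85%.
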